# 6. STUDY ASSESSMENTS

The investigator, a designated and appropriately trained staff member or the subject, will perform the study assessments according to the schedules noted below.

The same staff member should perform the assessments for a given subject throughout the study. If this becomes impossible, an appropriate designee with overlapping experience with the subject and study should perform the assessments.

The same lighting conditions and subject positioning should be used for all evaluations for a given subject.

## 6.1. Effectiveness Evaluations

## 6.1.1. Subject's Self-Assessment (SSA)

The SSA is the subject's assessment of the average overall severity of the target lesion at a particular time point and is not a comparison with the SSA at any other time point. The subject should NOT refer to any other evaluation to assist with these assessments.

At Visits 2 and 8, each subject will assess the target lesion using the scale below and report the one integer that best describes the average overall severity of the target lesion. At Visit 2, the subject must complete the SSA prior to the study medication application and prior to the PLA assessment. At Visit 8, the subject must complete the SSA prior to the PLA assessment.

An investigational center staff member other than the investigator must educate the subject on the SSA scale before each evaluation.

Subjects must be provided with a handheld mirror and/or a wall mirror (*i.e.*, a mirror that provides an unobstructed view of the target lesion).

To evaluate the target lesions an investigational staff member other than the investigator will identify the target lesion to the subject and direct the subject to assess the lesion. The staff member must not influence the subject's assessment.

| Subject's Self-Assessment  |  |  |  |
|--|--|--|--|
| Grade  | Descriptor   |  |  |
| 0  | None: no visible seborrheic keratosis lesion                   |  |  |
| 1 Mild: a slightly raised, light brown seborrheic keratosis lesion |  |  |  |
| 2  | Moderate: an obvious raised, brown seborrheic keratosis lesion |  |  |
| 3  | Severe: a prominent rough, dark seborrheic keratosis lesion    |  |  |
The study staff member will report the SSA grade the subject indicates in the source document. Both the subject and the study staff member must sign/initial the source document to indicate the subject performed the SSA as instructed.

The subject and the investigator must not discuss the subject's SSA grade and the subject must complete the assessment before the investigator performs the PLA (Section 6.1.2).

# 6.1.2. Physician's Lesion Assessment (PLA)

The PLA is the investigator's assessment of the average overall severity of the target lesion at a particular time point. The investigator should NOT refer to any other assessments to assist with these assessments.

At Visits 1, 2, 4, 6, 7 and 8, the investigator will assess the target lesion using the scale below and report the one integer that best describes the average overall severity of the target lesion. At Visit 2, and if appropriate Visit 4, the investigator must complete the PLA prior to the study medication application.

| Physician's Lesion Assessment |   |  |  |
|-------------------------------|---|--|--|
| Grade                         | Descriptor  |  |  |
| 0                             | Clear: no visible seborrheic keratosis lesion                               |  |  |
| 1                             | Near Clear: a visible seborrheic keratosis lesion with a surface appearance |  |  |
|                               | different from the surrounding skin (not elevated)                          |  |  |
| 2                             | Thin: a visible seborrheic keratosis lesion (thickness ≤1mm)                |  |  |
| 3                             | Thick: a visible seborrheic keratosis lesion (thickness >1mm)               |  |  |

At Visit 1 for the subject to be enrolled and at Visit 2 for the subject to be randomized the target lesion must have a PLA grade  $\geq$  2.

At Visits 2 and 8, the subject must complete the SSA (Section 6.1.1) assessment prior to the investigator performing the PLA.

#### 6.1.3. Lesion Dimensions

At Visit 1, at Visit 2 prior to randomization, at Visit 4 prior to any retreatment study medication application and at Visit 8 the investigator will measure the length, the width and, at Visit 1 ONLY, the thickness (height) of the target lesion using the ruler provided, or an equivalent.

The investigator must measure the length and width of the target lesion as follows:

- Length (*i.e.*, the length of the longest axis) measured in millimeters (mm) and reported to the nearest mm
- Width (*i.e.*, the length of the longest axis perpendicular to the length) measured in millimeters (mm) and reported to the nearest mm.

At Visit 1 for the subject to be enrolled and at Visit 2 for the subject to be randomized the target lesion must have:

- A length (longest axis) that is ≥7mm and ≤15mm
- A width (longest dimension perpendicular to the longest axis) that is ≥7mm and ≤15mm.

At Visit 2, and Visit 4, the length and width must be measured prior to any study medication application.

At Visit 1 ONLY, the investigator must measure the thickness (height) of the target lesion above the surrounding skin, in mm reported to the nearest 0.5mm.

At Visit 1 for the subject to be enrolled, the target lesion must have a thickness that is  $\leq 2.0$ mm.

## 6.2. Safety Evaluations

In addition to reporting adverse events throughout the study the investigator, a designated and appropriately trained staff member or the subject, will perform study following safety assessments according to the schedules noted below.

## 6.2.1. Local Skin Reactions (LSR)

The LSR assessment is the investigator's assessment of the signs and the subject's assessment of the symptoms associated with irritation at the target lesion site (*i.e.*, the target lesion and the skin immediately surrounding the target lesion exposed to study medication). The investigator and subject must NOT refer to any other evaluation to assist with these assessments. This is not a comparison with the assessment at any other time point.

### Local Skin Reactions:

- Signs (assessed by the investigator):
  - Erythema
  - o Edema
  - Scaling/dryness
  - Vesicles/bullae
  - Crusting
  - $\circ$  Erosion
  - Ulceration
  - Post-inflammatory hyper-pigmentation
  - Post-inflammatory hypo-pigmentation (does not include the superficial transient skin blanching/whitening related to the action of the study medications)
  - o Atrophy
  - Scarring.
- Symptoms (assessed by the subject):
  - Stinging/burning
  - Pruritus (itch).

At Visits 2-8, the investigator and the subject will evaluate the LSR signs and the LSR symptoms at the target lesion site respectively.

The investigator will assess the LSR signs for the target lesion site as follows:

- Visits 2 and 4:
  - Report the average severity for all signs prior to any study medication application
  - For the treated target lesion 20 (±4) minutes after the Application Completion Time, report the average severity for the following signs:
    - Erythema
    - Edema
    - Scaling/dryness
    - Vesicles/bullae.
- Visits 3 and 5-8:
  - Report the average severity for all signs.

The subject will assess the LSR symptoms for the target lesion site as follows:

- Visits 2 and 4:
  - Report the average severity over the previous 24 hours for all symptoms prior to any study medication application
  - For the treated target lesion, 10 (±4) minutes after the Application Completion Time, report the average severity of the LSR for all symptoms since completion of the study medication applications.
- Visits 3 and 5-8:
  - Report the average severity over the previous 24 hours for all symptoms.

The investigator should report the one integer that best describes average overall severity of each LSR sign for the target lesion site using the scale below.

An investigational staff member will identify the target lesion site being evaluated to the subject, educate the subject on the LSR scale before each evaluation and direct the subject to assess the site. The staff member should not influence the subject's assessment.

The study staff member will report the LSR grade the subject indicates in the source document. Both the subject and the study staff member must sign/initial the source document to indicate the subject performed the LSR as instructed.

The subject should report the one integer that best describes average overall severity of each LSR symptom for the target lesion site using the scale below:

| Local Skin Reactions |            |  |  |
|----------------------|------------|--|--|
| Grade                | Descriptor |  |  |
| 0                    | None       |  |  |
| 1                    | Mild       |  |  |
| 2                    | Moderate   |  |  |
| 3                    | Severe     |  |  |

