# 5.3.3. Visit 3 (Day 8)

This visit must occur 7 days (±4 days) after Visit 2.

At this visit, the investigator or designee will perform the following procedures:

- 1. Query the subject in a non-directive manner about any changes in her/his health since the previous visit and report all AEs on the appropriate form Section 7.2.1)
- 2. Query the subject about any changes in her/his concomitant therapies since the previous visit and report changes on the appropriate form (Section 4.5.2)
- 3. Confirm the subject continues to comply with all study restrictions, is eligible to continue in the study and has followed all study instructions (Section 5.5)
- 4. Confirm the location of the target lesion (Section 5.4)
- 5. Have the subject perform a Local Skin Reaction assessment for each of the symptoms for the target lesion (Section 6.2.1)
- 6. Perform an Local Skin Reaction assessment of the signs for the target lesion (Section 6.2.1)
- 7. Review the study instructions and restrictions with the subject (Section 5.5)
- 8. Schedule Visit 4 for Day 22.

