  - Apply white petrolatum (100%) United States Pharmacopeia (USP) along the orbital rim and at the medial and lateral canthi; gently stretch the periorbital skin between the thumb and forefinger at the time of petrolatum application to distend any periorbital rhytides (*e.g.*, "crow's feet") and ensure full coverage of the skin at the base of the rhytides to decrease the likelihood of tracking of the study medication towards the eye
  - Have the subject hold an absorbent pad in the appropriate area of the eye to absorb any excess study medication that might track away from the target lesion
  - Instruct the subject to keep both eyes closed during the entire study medication application procedure
- After the subject is properly prepared and positioned, thoroughly cleanse the target lesion by firmly rubbing with a cotton-tipped swab or absorbent wipe wetted with 70% isopropyl alcohol
- Hold the study medication vial away from her/his face and from the subject's face when opening and at all times
- Using the supplied applicator:
  - Wet the applicator with a quantity of study medication sufficient to wet the target lesion with a thin film
  - Using firm pressure and an application technique that is appropriate for the target lesion size (*e.g.*, dab and roll the applicator on smaller lesions; rub using a circular motion on larger lesions) apply the study medication to the target lesion for approximately 20-30 seconds
  - Minimize exposure to the surrounding normal skin and sensitive areas; you may have the subject assist by holding absorbent material (*e.g.*, clean absorbent wipe, clean paper towel, etc.) to prevent the study medication from migrating from the target lesion
  - During the application process remove excess study medication from the surrounding skin using a clean absorbent wipe
  - Ensure the target lesion is wet with study medication at the end of the 20-30 seconds
  - $\circ\,$  Allow the target lesion to remain undisturbed for approximately 60 seconds
  - o After approximately 60 seconds repeat the application process
  - Repeat the application/waiting cycle until the study medication has been applied to the target lesion 4 times.

Record the time the final application to the target lesion is completed as the Application Completion Time.

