#### 7.1. Definitions

#### 7.1.1. Adverse events (AE)

An AE is any untoward medical occurrence in a patient or clinical investigation subject administered a study medication(s) and which does not necessarily have a causal relationship with the study medication. An AE can therefore be any unfavorable and unintended sign or symptom associated with the use of a study medication (including an abnormal laboratory finding), whether or not related to the study medication.

Thus any new, clinically relevant worsening of an existing sign, symptom or disease, should be considered an AE.

Worsening of any of the target lesion assessments should be reported as an AE ONLY if the use of the study medication is interrupted or discontinued or if therapy is required to manage the event.

The investigator must, for any AE associated with a target lesion, question the subject in detail to determine if there are any confounding factors (*e.g.*, irritation by clothing or activity, sunburn) for any such AE.

Report any event that requires use of the eyewash kit [Section 5.7.6] as an AE for "eye irritation". For all AEs of this type:

- Contact the medical monitor (see contact information on Page 1, or in Section 7.2.2) immediately (within 24 hours)
- Unblind the study medication for the subject (Section 5.10.2)
- Arrange for the subject to be transported to the most appropriate hospital emergency room (ER) and provide the study medication identification information to the appropriate ER staff
- Follow the course of the AE
- Report the event as an SAE if appropriate (Section 7.1.2).

Every new episode or clinically relevant worsening of a chronic condition (*e.g.*, headaches, seasonal allergies, depression, and hypertension) should be reported as a separate AE, even if the condition is reported in the subject's medical history.

The investigator should, when certain, report a diagnosis rather than the signs, symptoms or clinically relevant abnormal laboratory values associated with the AE. Otherwise, signs, symptoms or abnormal laboratory values may be used to describe the AE.

Any CR abnormality discovered prior to the first study medication application should be reported as medical history, not as an AE.

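### The graded stinging/burning and itch ratings leave out the application itself and about 6 of the 7 nominal days after it

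*Combined protocol and SAP*

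**What the plan says.** Section 6.2.1 has the subject grade two symptoms, stinging/burning and pruritus, from 0 to 3. On an application day there is a pre-application rating over the preceding 24 hours and a post-application rating. The second is timed "For the treated target lesion, 10 (±4) minutes after the Application Completion Time", and the subject is then to "report the average severity of the LSR for all symptoms since completion of the study medication applications". At Visits 3 and 5 to 8 the instruction is "Report the average severity over the previous 24 hours for all symptoms".

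Section 5.7.6 fixes the clock: "Record the time the final application to the target lesion is completed as the Application Completion Time". In each pass the staff member is to "apply the study medication to the target lesion for approximately 20-30 seconds", with a wait of about 60 seconds between passes, and then "Repeat the application/waiting cycle until the study medication has been applied to the target lesion 4 times". Section 5.3.3 gives the Visit 3 window: "This visit must occur 7 days (±4 days) after Visit 2".

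On AEs, Section 7.1.1 states: "Worsening of any of the target lesion assessments should be reported as an AE ONLY if" study medication is interrupted or discontinued, or therapy is needed. Sections 7.1.4 and 7.2.1 start non-serious AE reporting at the first application, require at least 20 minutes of monitoring after completion, and have each visit ask an open question about health since the previous one. Section 9.2 tabulates local skin reaction (LSR) scores by study medication, without inferential tests.

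**The concern.** The introduction (Section 2.1) faults existing treatments for being painful and for sometimes needing anesthesia or analgesia, and presents A-101 as possibly avoiding both. Safety on the face is a stated objective (Section 3). The LSR symptom grades are the only graded record of how the treatment feels.

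Those grades start when the fourth pass ends, stop 6 to 14 minutes later, and resume 24 hours before the next visit. The plan has no diary, no rating during application and no worst-severity item. Each rating also asks for an average, so a short peak inside a window can be graded below its worst. A symptom that was never graded cannot be recovered at analysis, and the LSR tables could then understate what subjects felt.

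**Working it through.** The plan gives no figure for symptom coverage, so there is none to reproduce. The check is direct time arithmetic.

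**Inputs**
- Passes: 4, each 20 to 30 s; wait between passes about 60 s (5.7.6)
- Completion Time: end of the final pass (5.7.6), so three waits precede it
- Post-application rating: 10 ± 4 min, that is 6 to 14 min after completion (6.2.1)
- Recall at Visits 3 and 5: 24 h = 1,440 min (6.2.1)
- Visit 3: 7 ± 4 days, that is 3 to 11 days after Visit 2 (5.3.3)
- Visit 4: 21 ± 4 days after Visit 2 (5.3.4)
- Visit 5: 28 ± 4 days. Section 5.3.5 omits the reference visit. Visit 2 is assumed, since 5.3.2 schedules later visits from it.

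**Application time outside every symptom window** = 4 × pass + 3 × wait
- Short passes: 4 × 20 + 3 × 60 = 260 s = 4.3 min
- Long passes: 4 × 30 + 3 × 60 = 300 s = 5.0 min

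**Ungraded time after the first application** = interval − 1,440 min − about 10 min

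| Visit 3 at | Interval (min) | Ungraded (min) | Ungraded (days) | Share |
|---|---|---|---|---|
| 3 days | 4,320 | 2,870 | 1.99 | 66% |
| 7 days | 10,080 | 8,630 | 5.99 | 86% |
| 11 days | 15,840 | 14,390 | 9.99 | 91% |

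Using 6 or 14 minutes in place of 10 does not change the days by more than 0.01.

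**After retreatment**
- Nominal: 28 − 21 = 7 days, of which about 6 are ungraded
- Widest: Visit 4 at 17 days and Visit 5 at 32 days give 15 days, of which about 14 are ungraded

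**Can AE reporting fill the gap?**
- The open question at each visit covers the whole interval, so a subject may mention burning on an unrated day.
- Section 7.1.1 then restricts what is recorded if the event is a worsening of a target-lesion assessment. That term is not defined. The visit procedures in 5.3.2 to 5.3.7 describe the LSR symptom rating as made for the target lesion, so a site could apply the restriction to it. Section 6.2.1 describes the LSR as covering the lesion site including exposed surrounding skin, so a site could also decide otherwise.
- Even a recorded AE carries its own severity term (7.1.5), not a 0 to 3 LSR grade.

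**The case against.** Much of the case on the other side stands.

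- **AE reporting.** A reader might infer that severe treatment pain is barred from being an AE. The documents do not support that. Section 7.1.1 sets a condition: events that interrupt or stop study medication, or need therapy, are reportable. The same section counts any new, clinically relevant worsening of a symptom as an AE, and pain as such is not a listed LSR symptom.
- **Treated symptoms.** Section 4.5.2 requires new concomitant therapies, including over-the-counter drugs, to be recorded, and links them to AE reporting unless the reason is prophylactic or non-medical. An analgesic taken for burning is therefore captured on any day.
- **The 10-minute rating.** Under 5.7.6 the remaining solution stays in place until just before this rating. Severe burning that continued without a break would be graded there. What escapes is stinging that ends by completion, or that begins after the rating and is gone more than 24 hours before the next visit.
- **Time course.** A reader might infer that the ratings miss the period when reactions are most likely, or that 86% of symptoms go unseen. The documents give no symptom time course; 86% is a share of clock time. The windows are the same in all three arms, so blurring of arm differences is a possibility that the documents cannot demonstrate.
- **Side effects of a change.** Section 5.7.6 compares Visit 4 and Visit 3 LSR grades when deciding on retreatment. A second Visit 3 rating would make that comparison ambiguous, and replacing an average with a worst grade would lose comparability with the pre-application rating. Both objections are sound against replacing items. Adding items, and naming the grade that 5.7.6 uses, answers them.

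**Conclusion.** The point holds in a limited form. The application (about 4.3 to 5 minutes) and about 6 of the 7 nominal days after it fall in no graded symptom window. For the first treatment the ungraded share is 66% to 91% across the allowed Visit 3 timing. Severe stinging or itch that is tolerated to completion, untreated and confined to those periods can go ungraded. Whether it is reported as an AE depends on how a site reads an undefined term in Section 7.1.1.

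This rests on the stated pass and wait times, on Completion Time being the end of the fourth pass and, for the retreatment figures only, on Visit 5 being timed from Visit 2. How many subjects would be affected cannot be estimated from the documents. The consequence is confined to the descriptive tolerability data; the Physician's Lesion Assessment endpoint and the study's power are untouched. It is a worthwhile, low-cost improvement rather than a defect that threatens the trial.

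**What to change.** In Section 6.2.1 and on the LSR source form, keep every existing rating and add, for each of the two symptoms:

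- (a) at the 10-minute post-application rating, the worst severity since the start of the study medication application;
- (b) at Visit 3, and at Visit 5 for retreated subjects, the worst severity since the last application.

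In Section 9.2, tabulate the new items descriptively by treatment group. In Section 5.7.6, state that the Visit 3 versus Visit 4 comparison continues to use the existing 24-hour symptom grade, so that the retreatment rule is unchanged. Visits 6 to 8 stay as they are. Separately, one sentence in Section 7.1.1 could say whether LSR symptoms count as target-lesion assessments.

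The cost is 4 extra integers for a subject treated once (2 symptoms × 2 ratings) and 8 for a retreated subject (2 × 4), with the matching CRF fields. No visit or procedure is added. The drawback is that recall over a week is less exact than over 24 hours, which is why the 24-hour item stays beside it.

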## 6.2.2. Vital signs

Vital signs will be measured by a qualified staff member at Visit 1, Visit 2 prior to randomization, and at Visit 8. The following items will be measured:

- Body temperature
- Pulse rate
- Respiration rate
- Blood pressure (systolic and diastolic) after the subject sits quietly for at least 5 minutes
- Height (at Visit 1 only)
- Weight (at Visit 1 only).

Any measure that is, in the opinion of the investigator, abnormal AND clinically relevant (CR) must be recorded as history if found prior to the first study medication application or as an AE if found after the first study medication application begins (Section 7.1).

A systolic blood pressure >140mm Hg or a diastolic blood pressure >90mm Hg is considered abnormal and therefore must be defined as CR or not clinically relevant (NCR) on the comments page of the CRF.

A weight >300 lbs. is considered abnormal and therefore must be defined as CR or NCR on the comments page of the CRF.

